The TPI can be modified – Modified Time Principle Induction (MTPI) – by administering a sedative and a neuromuscular blocking agent nearly simultaneously to minimize the likelihood of awareness of muscle paralysis before a loss of consciousness (Figure 1). In CI, a propofol bolus (1-2 mg/kg) will typically result in apnea in about 60 seconds. Attempted mask ventilation, followed by administration of NMBD, will take over 3 minutes, as it takes about 3 minutes to reach maximal muscle paralysis. If an intubation attempt is unsuccessful followed by an unsuccessful supraglottic airway (SGA) insertion, this will likely encompass an additional two minutes of time. If sugammadex (16 mg/kg) is given with return of adequate spontaneous breathing occurring 2 minutes after administration, the total apnea time will be 8 minutes. In a MTPI, patients would receive a non-depolarizing NMBD first, like rocuronium (0.6 mg/kg), immediately followed by a sedative-hypnotic, like propofol 1-2 mg/kg, without waiting for the onset of muscle weakness. Once apnea occurs, attempted intubation starts. If the intubation is not successful, it is followed by attempted mask ventilation, and then SGA ventilation (each step takes 1 minute). If none of them are successful, sugammadex is given. A total of 5 minutes of apnea time is needed to regain adequate spontaneous breathing. The apnea oxygenation time is shortened by 3 minutes or by 43%. Therefore, the need for invasive airway management will likely be reduced. Since the

sedative-hypnotic and muscle relaxant are administered simultaneously, the awareness of paralysis before loss of consciousness is unlikely to occur.

[figure not shown]

Figure 1. Schematic demonstration of intubating conditions created by Classic Induction vs. Modified Time Principle Induction (MTPI) with propofol and rocuronium. Propofol concentration in plasma in the brain (red line). Rocuronium induced muscle paralysis for classic induction (blue solid line) and Modified Time Principle Induction (green solid line). Muscle paralysis reversal after Sugammadex after MTPI (green dotted line) and classic induction (blue dotted line).

2. Hypothesis

Intubation conditions between patients receiving MTPI and CI are comparable. We will test this hypothesis by comparing time to intubation between the two techniques.

3. Specific aims

- 3.1 To assess and compare the conditions for tracheal intubation obtained with MTPI and that obtained with CI.

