- 3.2. To compare the efficiency of tracheal intubation with the two induction techniques.
- 3.3. To determine the rate of awareness during induction and post-operative recall of muscle weakness.

4. Patient enrollment

This study will be carried out in the main operating rooms at Memorial Hermann Hospital in the Texas Medical Center (TMC). The study team will approach the patients in the respective preoperative holding area after reviewing their medical records to determine eligibility. Once the study team believes that a particular patient is eligible to participate in the study, the study team will provide that patient with detailed information about the study and obtain informed consent from the patient.

4.1. Inclusion criteria:

- I. 18 or older years of age
- II. BMI $>30 \text{ kg/M}^2$ or Mallampati class III or IV
- III. Requiring general anesthesia and endotracheal intubation

4.2. Exclusion criteria:

- I. Acute and chronic respiratory disorders, including COPD and asthma
- II. ASA physical status classification $> \text{III}$
- III. Emergency surgery
- IV. Induction requiring cricoid pressure

- V. Patients requiring awake intubation
- VI. Pregnant women
- VII. Patients who require an induction dose of propofol less than 1 mg/kg
- VIII. Untreated ischemic heart disease
- IX. Contraindication to mask ventilation
- X. Allergy to propofol, rocuronium, or Sugammadex
- XI. Induction requiring succinylcholine

Randomization and Blinding

Patients will be randomly assigned to the MTPI group and the Classic Induction group (control) using an online randomization program (<https://www.randomizer.org/#randomize>). A concealed envelope will be opened prior to induction. A study arm specific handout of induction instructions will be handed to the anesthesia provider. Laryngoscopy will be done with C-MAC and the entire laryngoscopy and entire intubation procedure will be recorded and saved. Study team members converting the video recorded data to digital data will be blind to the interventions. Once the study is completed and the digital data is collected, the study team members will be unblinded.

5. Outcomes

5.1 Primary outcome: The time between laryngoscope insertion into mouth and the onset of ventilation after tracheal intubation with MTPI vs. CI as visualized with C-MAC

5.2 Secondary outcomes:

5.2.1 The success rate of first attempted tracheal intubation, number of attempts, and failed intubation.

- 5.2.2 The best glottic view

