arms of the study are those used for routine anesthesia care. In both study arms, dosing of medications for induction of anesthesia is standardized (lidocaine 1 mg/kg, fentanyl 1-2 mcg/kg, propofol 1-2 mg/kg, and rocuronium 0.6 mg/kg). The only difference between the two arms will be the timing of the medication administration, and the order in which medications are administered. The documentation of induction and intubation will be the same as that of the MTPI group. Vital signs and other parameters will continuously be recorded in the intraoperative record. Emergence and extubation are not protocolized. Once the patient arrives in the PACU, the study team will assess the patient 30 min after arrival and attempt to conduct a post-operative survey (see PACU Patient Survey).

7. Data acquisition and analysis

All ventilatory settings and measured parameters displayed on the operating room ventilator (Datex Ohmeda AS/5, Helsinki, Finland), including expired tidal volume, flow waveforms, end-tidal carbon dioxide partial pressure, exhaled carbon dioxide waveforms, and vital signs displayed on the monitor will be recorded intra-operatively in the electronic medical record and video recorded from the time of pre-oxygenation and 5 minutes after intubation. Specific time points that will be collected are induction time, onset of apnea, beginning of intubation attempt, and time to successful intubation (identified by time between laryngoscope insertion into the mouth and the onset of ventilations after tracheal intubations with MTPI vs. CI with C-MAC).

8. Predicted outcome and its significance

The study team assumes that MTPI will be non-inferior to CI in the rate of 1st attempt tracheal intubation success. Additionally, we predict no significant difference in intubation time, glottic view, rate of successful intubation, rate/severity of injury associated with tracheal intubation, and the rates of awareness of muscle paralysis before loss of consciousness using the two different types of approaches. The study team predicts that MTPI will create similar intubating conditions compared to CI and will shorten the apnea time by 3 minutes (a reduction in apnea time by 37.5%) if a “cannot intubate and cannot ventilate” scenario is encountered and sugammadex rescue is used to reverse muscle paralysis. By shortening apnea time, we expect that MTPI would improve difficult airway management and therefore patient outcomes.

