Positive outcomes expected from this study include increased efficiency in induction and intubation. Another benefit would be no longer needing to mask ventilate. Since 60% of aspiration occurs during mask ventilation, avoiding mask ventilation will significantly reduce aspiration rates. Also, a high dose (1.2 mg/kg) of rocuronium recommended for rapid sequence induction may not be needed. Furthermore, it is known that succinylcholine is associated with increased muscle aches, cardiac arrest, and mortality rates. The new method of modified time principle induction being done in this study may lead to a decreased need for succinylcholine as an option for muscle paralysis.

9. Sample Size Calculation

The primary outcome is time between laryngoscope insertion into mouth and the onset of ventilation after tracheal intubation in CI vs. MTPI as visualized with C-MAC. Among successful intubations, laryngoscopy time with a C-MAC averaged 46 seconds (95% CI, 40-

51).¹⁵ We assume the time required for tracheal intubation with the two induction approaches using a C-MAC is not significant if the time between the two approaches is smaller than 15 seconds. With 80% power at 0.05 significance, a total sample size is 130 patients, with 65 patients in each arm. To account for a drop rate of 15%, we will enroll a total of 154 patients.

10. Risk Assessment

10.1. Potential complications associated with induction and intubation are expected to be the same between the two groups. In another words, this study would be unlikely to add risk or reduce the existing potential risk of induction and intubation.

10.2. Adverse effects of medications: Propofol and fentanyl are routinely used for anesthesia care. We will exclude the patients who are allergic to these two medications. Midazolam is routinely used as pre-medication. Any risk associated with these three medications will not be altered due to the study. All other medications will not be restricted to use for patient care including antiemetics.

10.3. Patient awareness of muscle weakness before a loss of consciousness is a potential risk of the study. However, previous studies using a time principle induction have not demonstrated this in both the operating room and emergency room settings. Therefore, we do not anticipate any increased risks of awareness of muscle weakness in the study group when compared to the control group.

11. Data Safety Monitoring

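### The plan sets out to show that MTPI and classic induction are comparable on intubation time, but it compares no confidence limit with its 15 s figure and ties its 80% power to no stated test or SD.

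*Combined protocol and SAP*

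**What the plan says.** Section 2 states the hypothesis: "Intubation conditions between patients receiving MTPI and CI are comparable". It continues: "We will test this hypothesis by comparing time to intubation between the two techniques". Section 5.1 makes the time from laryngoscope insertion to the onset of ventilation the primary outcome.

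Section 7 is headed as covering data acquisition and analysis, but it describes only recording: "Specific time points that will be collected are induction time, onset of apnea, beginning of intubation attempt, and time to successful intubation". It names no test, estimate, interval or decision rule.

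Two other sentences bear on the result for time. Section 8 says "we predict no significant difference in intubation time, glottic view, rate of successful intubation". Section 9 assumes that the time required with the two approaches "is not significant if the time between the two approaches is smaller than 15 seconds", and then gives 80% power, 0.05 significance, 65 patients per arm and 154 enrolled after a 15% allowance for drop-out. Section 9 states no SD, sidedness or test. Its only data input is that "laryngoscopy time with a C-MAC averaged 46 seconds", with a 95% confidence interval of 40 to 51.

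Non-inferiority is mentioned for this trial's own comparison only in Section 8, for a secondary outcome and without a margin: "The study team assumes that MTPI will be non-inferior to CI in the rate of 1st attempt tracheal intubation success".

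**The concern.** A claim of comparability has to exclude a difference large enough to matter. A non-significant test does not do that, since it may only mean that the estimate is imprecise. An observed difference under 15 s does not do it either, because the confidence interval around it can extend well past 15 s.

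The 15 s may have been meant as a margin, but the sentence judges the difference itself and no confidence limit is set against it. Read as worded, the trial could report the techniques as comparable while its own data remain compatible with MTPI being slower by more than 15 s. The chance of that wrong conclusion is not fixed by the design. It depends on an SD that the plan does not state, and under a reading based on non-significance it grows as evaluable patients are lost.

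**Working it through.** **Inputs from Section 9:** 15 s; 80% power; 0.05; 65 per arm; 15% drop-out; 154 enrolled. **Not given anywhere:** SD, sidedness, test.

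**1. The plan's own figures.** The drop-out step reproduces: 65 / 0.85 = 76.5, so 77 per arm, or 154. The 65 per arm cannot be reproduced without an SD, so it is solved backwards. By the normal approximation, n = 2 × [SD × (1.960 + 0.842) / 15]². At n = 65 this gives SD = 15 × √32.5 / 2.802 = 30.5 s, and the exact t calculation gives 30.3 s. Other tests imply other SDs for the same 65 per arm (t-based):

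| Test assumed | SD giving 80% power |
|---|---|
| Two-sided 0.05, or non-inferiority at one-sided 0.025 | 30.3 s |
| Non-inferiority at one-sided 0.05 | 34.2 s |
| Equivalence, 90% interval within ±15 s | 29.1 s |
| Equivalence, 95% interval within ±15 s | 26.2 s |

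The sample size therefore does not reveal which design was intended.

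**2. Can the SD be recovered from the cited mean?** The interval of 40 to 51 has a half-width of 5.5 s, so SE = 5.5 / 1.96 = 2.8 s. SD = SE × √n, and the n of that source is not given. SDs of 20, 25, 30.3 and 40 s would need n of about 51, 79, 117 and 203. The figure is cited to reference 15, and the reference list ends at 14. The range 20 to 40 s is therefore an assumption.

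**3. What each reading allows.** With 65 per arm, the SE of the difference is SD × √(2/65) = 0.1754 × SD. With t(0.975, 128 df) = 1.979, the 95% half-width h is 0.347 × SD.
- The largest upper limit that goes with a non-significant result is 2h.
- An observed difference just under 15 s has an upper limit of about 15 + h.
- Non-significance at a true 15 s is one minus the power of the two-sided t-test.
- Power of the confidence-limit rule (upper 95% limit below 15 s) is taken at zero true difference.

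| SD (s) | h (s) | Non-significant at a true 15 s | 2h (s) | 15 + h (s) | Power of the confidence-limit rule |
|---|---|---|---|---|---|
| 20 | 6.9 | 1% | 13.9 | 21.9 | 99% |
| 25 | 8.7 | 8% | 17.4 | 23.7 | 92% |
| 30.3 | 10.5 | 20% | 21.0 | 25.5 | 80% |
| 35 | 12.1 | 32% | 24.3 | 27.1 | 68% |
| 40 | 13.9 | 44% | 27.8 | 28.9 | 56% |

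If the true slowing is 15 s, the estimate is centred on 15 s, so an observed difference under 15 s occurs 50% of the time at every SD shown. The confidence-limit rule is met 2.5% of the time at a true 15 s, whatever the SD.

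**4. Dependence on evaluable numbers, at SD 30.3 s.** Non-significance at a true 15 s is 14% with 77 per arm, 20% with 65 and 31% with 50. The confidence-limit rule stays at 2.5% throughout.

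**5. Two-sided equivalence, at SD 30.3 s and zero true difference.** With 65 per arm, power is about 75% with a 90% interval and 60% with a 95% interval. For 80% power, 71 per arm (142) or 87 per arm (174) are needed.

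**The case against.** The best defence is that 15 s is plainly a margin, and that the power statement next to it implies a hypothesis test rather than a rule on the point estimate. On that view 65 per arm is exactly right for non-inferiority at one-sided 0.025 with an SD near 30 s, the Section 8 sentence is only a prediction, and what is missing is specification rather than design. That may be what was intended, but the text does not say so. The 50% figure follows from the sentence as worded. If a margin was meant, the amendment only writes it down.

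Several points on size are fair:
- The harm from the non-significance reading depends on the SD. Since 2h is below 15 s when SD < 7.5 / 0.347 = 21.6 s, a non-significant result with an SD below that value would itself exclude a 15 s slowing. The plan gives no basis for assuming so small an SD.
- The 20% at SD 30.3 s is simply the type II error of a two-sided test with 80% power.
- Fifty evaluable per arm is a hypothetical loss of 35% from 77, well beyond the planned 15%.

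It is also fair that words such as comparable suggest a two-sided claim, and that intubation times may be skewed. The choice between non-inferiority and equivalence belongs to the sponsor, and the handling of skewness and of failed intubations should be settled when the rule is written. None of this supplies the missing criterion.

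**Conclusion.** The concern holds and must be fixed. The primary claim of comparability has no defined success criterion and no controlled error rate. No arithmetic error is alleged: 154 follows from 65 per arm, and 65 per arm is attainable under several designs with an unstated SD of roughly 26 to 34 s.

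If non-significance is read as comparability, a true 15 s slowing would pass about 1% to 44% of the time over SDs of 20 to 40 s. If an observed difference under 15 s is read that way, it would pass half the time. These figures assume 65 evaluable per arm, equal SDs and a two-sample t-test; the SDs are assumed. The textual gap depends on none of these assumptions.

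**What to change.** Before unblinding, amend Section 9 to name 15 s as the margin. MTPI should be declared not slower only if the upper limit of the two-sided 95% confidence interval for the mean difference in time (MTPI minus classic induction) is below 15 s. Align Sections 2 and 8 with this rule, and state that a non-significant difference will not be read as comparability. State the SD and test actually used to reach 65 per arm, and restate the power for the new rule.

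If a two-sided claim is intended, require the interval to lie within ±15 s, say whether it is the 90% or the 95% interval, and restate the power accordingly.

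Report first-attempt success as a risk difference with a 95% confidence interval, and make no non-inferiority claim for it because no margin is set. With 65 per arm and equal true rates assumed at 80, 85, 90 or 95%, the half-width 1.96 × √[2p(1 − p)/65] is about 14, 12, 10 or 7 percentage points.

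The blinding section says: "Once the study is completed and the digital data is collected, the study team members will be unblinded". The Section 15 milestones put completion in January 2025. If unblinding has already happened, report the interval against 15 s and label the criterion as set afterwards.

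**Cost.** The change is wording in Sections 2, 8 and 9, and adopting the one-sided rule does not itself require more patients. The criterion is stricter: at SD 30.3 s the observed slowing must be under about 15 − 10.5 = 4.5 s. The stated power may also fall, to 68% at SD 35 s or 56% at 40 s. Restoring 80% there would take about 87 or 113 per arm. A two-sided claim at SD 30.3 s would need about 142 or 174 evaluable patients, against the 130 planned.

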11.1. A data safety monitor will review the trial protocol and the accumulated data on an ongoing basis for the duration of the trial. This individual will be monitoring the

benefits and risks to the participants of the trial in order to protect patient safety, credibility of the trial and validity of the study results.

- 11.2. The data safety monitor will be unaffiliated with the study and will have no financial, scientific, or other conflict of interest with the trial. The data safety monitor will have experience in the proper conduct of clinical trials and statistical knowledge in order to evaluate the results of the data.
- 11.3. The data safety monitor will perform data reviews at 30, 60, 90, 120, and 143 patients, or sooner if indicated.
- 11.4. Specific roles of the data safety monitor include oversight and analysis of study data to ensure continuing safety of trial participants, efficacy of the study intervention, and data integrity. By reviewing the data as it accumulates, the data monitor can identify significant trends or issues, and provide recommendations for changes in the study as needed.

12. Reporting of Adverse Events or Unanticipated Problems involving Risk to Participants or others

The study team does not anticipate increased risk of intraoperative events or other complications associated with this study as compared with routine care. Any adverse events and complications occurring in either group will be reported in the Data Collection Sheet.

- 12.1. Adverse events (AE) will be obtained and documented by the investigators performing data collection and by questioning or examining the patient. All new complaints and symptoms (i.e., those not existing before the signing of informed consent) will be recorded on the AE CRF.

12.2. AE's will be characterized in terms of their start and stop dates, start and stop times, intensity, action taken, relationship to research study, subject outcome, and whether the AE led to an SAE.

12.3. The study team will perform a review of adverse events after enrollment of 20 subjects.

13. Privacy/Confidentiality Issues

Measures will be taken to prevent lapses in confidentiality from occurring. Only key study personnel will have access to identified information. Exported and extrapolated data will be stored on a password protected UTHealth computer that only key study personnel can access. Any paper records will be kept in a drawer with a lock within [name] office.

14. Follow-up and Record Retention

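### Does the monitor's efficacy remit in Section 11.4, with five reviews before 154 patients, leave the final 0.05 level unprotected?

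*Combined protocol and SAP*

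**What the plan says.** Section 11.4 says the monitor's roles "include oversight and analysis of study data to ensure continuing safety of trial participants, efficacy of the study intervention, and data integrity". It adds that, as data accumulate, "the data monitor can identify significant trends or issues, and provide recommendations for changes in the study as needed". Section 11.3 sets the timing: "The data safety monitor will perform data reviews at 30, 60, 90, 120, and 143 patients, or sooner if indicated". Section 11.1 has the monitor watch the "benefits and risks to the participants of the trial in order to protect patient safety", and also names the trial's credibility and the validity of its results. On who the monitor is, Section 11.2 says: "The data safety monitor will be unaffiliated with the study and will have no financial, scientific, or other conflict of interest with the trial". It also asks for trial experience and statistical knowledge.

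Section 9 plans one comparison of intubation time. It gives a 15 s limit, 80% power and a 0.05 level, with 65 patients per arm (130 in all), raised to 154 for a 15% drop rate. It mentions no interim analysis. Under Randomization and Blinding: "Once the study is completed and the digital data is collected, the study team members will be unblinded". The aim is comparability. Section 2 states "Intubation conditions between patients receiving MTPI and CI are comparable", and Section 8 says "we predict no significant difference in intubation time".

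**The concern.** Three features together look like an uncontrolled sequential design. Efficacy is named in the monitor's analysis. There are five scheduled reviews and possibly unscheduled ones. The monitor may recommend changes. Yet there is no boundary, no split of the 0.05 level, no statement that the reviews are for safety only, and none that early claims are excluded. The delayed unblinding covers study team members and does not mention the monitor.

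The comparability aim sharpens the worry. In a superiority trial a small interim sample seldom gives a striking result. Here the welcome finding is no difference, which a small sample produces easily. If such a reading led to an early claim or an early stop, neither the 0.05 level nor the 15 s limit in Section 9 would support it.

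**Working it through.** **1. The plan's own figures.** 65 / 0.85 = 76.5, so 77 per arm and 154 in total, as Section 9 states. All five reviews fall earlier: 30, 60, 90, 120 and 143 of 154 are 19%, 39%, 58%, 78% and 93%. The 130 cannot be reproduced because no SD is given.

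**2. SD implied by Section 9 (an assumption).** From 15 s, 65 per arm and 80% power, SD = 15 / [(z for the level + z for the power) × √(2/65)], with √(2/65) = 0.1754. The documents do not name the test, so four readings are shown:

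- Difference, two-sided 0.05: 15 / [(1.960 + 0.842) × 0.1754] = 30.5 s
- One-sided 0.05: 15 / [(1.645 + 0.842) × 0.1754] = 34.4 s
- Two one-sided tests at 0.05 each, true difference 0: 15 / [(1.645 + 1.282) × 0.1754] = 29.2 s
- Two one-sided tests at 0.025 each, true difference 0: 15 / [(1.960 + 1.282) × 0.1754] = 26.4 s

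**3. The plan as written.** One final test is made at its nominal level. Suppose the monitor stops only for harm, taken for illustration as Z < −1.96 against the new technique at any of the five reviews, with a final claim at Z > 1.96. Simulation under the null (independent increments at the review counts) gives a false claim rate of 2.49% against 2.5%. Harm stops can only remove false claims of non-inferiority.

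**4. The hypothetical misuse.** Suppose similarity within 15 s were tested by two one-sided tests, unadjusted, at all five reviews and at 154, and claimed at the first success. The true difference is set at 15 s. One million simulated trials, SD 26.4 to 34.4 s, with and without the 15% drop:

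| Level per side | Final test only | Any of six looks |
|---|---|---|
| 0.05 | about 5% | about 9-11% |
| 0.025 | about 2.5% | about 4-6% |

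Testing repeatedly for a *difference* at two-sided 0.05 over the same six looks gives about 14.7%, and one-sided 2.5% testing gives about 7.4%. The first concerns false claims of difference. The second counts rejections at 30 patients, where two-sided similarity cannot be shown (step 5). Neither measures the risk for this aim.

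**5. The first review.** Half-width = z × SD × √(2/m), with m = 15 per arm, or 30 × 0.85 / 2 = 12.75 after the drop. Each SD is paired with the level that produced it:

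- Smallest: 1.645 × 29.2 × √(2/15) = 17.5 s
- Largest: 1.960 × 30.5 × √(2/12.75) = 23.7 s

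Both exceed 15 s, so even an observed difference of zero could not establish similarity. Absence of significance would mean little there. With a true 15 s delay, the chance of a two-sided p of at least 0.05 is about 66% (SD 26.4 s, 15 per arm) to 80% (SD 34.4 s, 12.75 per arm).

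**6. The text side by side.** Section 11 is headed as safety monitoring. Section 11.1 makes the validity of the results part of the monitor's purpose. Section 11.4 gives a power to recommend, and none to stop the trial or declare a result. Its mention of efficacy names no outcome, comparison or test. Section 9 has one level and one sample size, Section 15 runs to 154 patients, and the study team is unblinded at completion. The consistent reading is a single final analysis.

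**The case for a change.** The best case for acting is that independence and statistical knowledge settle who looks at the data, not what may be concluded. Efficacy is named, early reviews are frequent, and a reader of the final report could not tell from the protocol whether those reviews might have shaped the result. A sentence excluding early claims would need no patients and no reviews, and would leave the 0.05 level alone.

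The factual part stands: the documents are silent, and the blinding sentence does not cover the monitor. Such a sentence would do no harm. It would not alter what the plan does, however. The error rates in step 4 need three things the plan lacks: a test at each review, a threshold, and authority to claim on crossing it. Nor should the mention of efficacy be read as improper in itself. A monitor looking for harm may need intubation time by arm, because a slower intubation is both the efficacy result and a safety signal.

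The review at 143, set against 154 enrolled, is at most a clerical matter. 130 × 1.10 = 143, so it may be left from another enrolment target, but that is inference. On the current text it is simply a fifth review before the end.

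**Conclusion.** No change is called for. The wording of Section 11.4 is broader than it need be, but this is missing detail that a competent monitor and analyst would fill in the ordinary way: review for harm, then one final analysis at the planned level. On that reading the added error is zero, and 130 and 154 are unaffected. The inflation to about 9-11% (against 5%), or about 4-6% (against 2.5%), belongs to a procedure the plan does not contain. It also rests on SDs of 26.4 to 34.4 s that are back-solved rather than stated, and on review counts taken as enrolled patients. The conclusion assumes that the monitor acts within the advisory role the text gives and that no similarity claim is made before the study is complete. If an early claim were in fact made, this judgement would no longer hold.
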